## 5.2 Definition of Dose-Limiting Toxicity

Dose escalation will be based on DLTs observed during the first cycle of treatment.

**5.2.1** Grade  $\geq 3$  non-hematologic toxicity will be considered dose limiting, with the following exceptions:

- 5.2.1.1 Grade 3 fatigue lasting  $\leq 7$  days.
- 5.2.1.2 Grade 3 diarrhea will only be considered dose limiting if it is caused by colitis or, if after 72 hours, it is refractory to treatment. Grade 4 diarrhea will be dose limiting.
- 5.2.1.3 Grade 3 nausea and vomiting will only be considered dose limiting if after 72 hours it is refractory to maximal anti-emetic therapy and unable to be corrected to Grade  $\leq 2$  or baseline.
- 5.2.1.4 Grade 3 rise in creatinine, not corrected to Grade 1 or baseline after intravenous fluids within 24 hours, will be considered dose limiting. All Grade 4 rises in creatinine will be dose limiting.
- 5.2.1.5 Grade 3 electrolyte toxicities unable to be corrected to Grade 2 or baseline within 24 hours will be considered dose limiting.
- 5.2.1.6 Grade 3 liver function test (ALT, AST, alkaline phosphatase, total bilirubin) abnormalities in the absence of clinical signs of hepatic dysfunction (lethargy, confusion, anorexia, pruritus, tremor) that persist  $\leq 3$  days will not be considered dose-limiting.

**5.2.2** Grade 4 hematological toxicity

- 5.2.2.1 Neutropenia: Grade 4 neutropenia of any duration accompanied by fever or infection will be considered dose limiting. Grade 4 neutropenia for  $>5$  days without fever or infection will be considered dose limiting. Transient neutropenia ( $\leq 5$  days) without fever or infection will not be considered dose-limiting. Twice weekly blood draws will be needed (after onset of grade 4 neutropenia) to monitor duration of neutropenia for the first 2 cycles. On subsequent cycles (cycle 3 and beyond), weekly blood draws will be monitored after onset of grade 4 neutropenia.
- 5.2.2.2 Thrombocytopenia: Grade 4 thrombocytopenia will be considered dose limiting. Grade 3 thrombocytopenia associated with bleeding will be considered dose limiting.
- 5.2.2.3 Anemia: Grade 4 anemia will be considered dose limiting.

**5.2.3** Any neurotoxicity Grade  $\geq 2$  that is not reversible to a Grade  $\leq 1$  within 2 weeks will be considered dose limiting.

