**If study treatment is held for >42 days, the patient will go off study.**

While doses are being held, the patient will continue to progress through the treatment cycle. When the patient is able to resume treatment, restart drug administration as soon as possible based on the cycle schedule. Omit any missed doses.

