### **Nivolumab and Ipilimumab Dose Delays**

Below are dose delay and management tables for nivolumab and ipilimumab, indicating when study drug should be held or discontinued due to nivolumab or ipilimumab –specific adverse events.

ALL OTHER EVENTS	Management/Next Dose for Nivolumab and Combination Nivolumab/ipilimumab
≤ Grade 1	No change in dose. Continue treatment.
Grade 2	Hold until ≤ Grade 1 OR baseline (exceptions as noted below)
Grade 3	Off nivolumab/ipilimumab therapy. For immune-related adverse events, hold nivolumab and ipilimumab until ≤ Grade 1 OR baseline; resume at the same dose level (exceptions as noted below).
Grade 4	Off nivolumab and ipilimumab therapy (exceptions as noted below)

Recommended management: As clinically indicated

- Any adverse event, laboratory abnormality, or intercurrent illness which, in the judgment of the investigator, presents a substantial clinical risk to the subject with continued study drug dosing should discontinue nivolumab/ipilimumab treatment.
- Any grade 2 drug-related uveitis or eye pain or blurred vision that does not respond to topical therapy and does not improve to Grade 1 severity within the re-treatment period OR requires

systemic treatment should discontinue nivolumab/ipilimumab treatment.

- Any grade 3 or 4 drug-related laboratory abnormality or electrolyte abnormality, that can be managed independently from underlying organ pathology with electrolyte replacement, hormone replacement, insulin or that does not require treatment does not require discontinuation.
- Patients requiring > two dose delays for the same event should go off protocol therapy. Patients may be dose-delayed for evaluation and restarted depending on results.
- Please note that grading and for hypophysitis with symptoms of headache, visual or neurologic changes or radiologic evidence of pituitary enlargement and other CNS events such as aseptic meningitis or encephalitis should be considered grade 3 events.

Skin Rash and Oral Lesions	Management/Next Dose for Nivolumab and Combination Nivolumab/ipilimumab
≤ Grade 1	Continue therapy. No change in dose.*
Grade 2	Monitor weekly until 1≤ Grade. May initiate intermediate potency topical steroids (and treatment for pruritis if needed). Resume at same dose level.
Grade 3	Hold* until ≤ Grade 1. Resume at same level at investigator discretion.
Grade 4	Off nivolumab and ipilimumab treatment.

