Grade 3	Hold until ≤ Grade 1. Resume at same dose level.
Grade 4	Off treatment

Endocrine: Hypophysitis Adrenal Insufficiency	Management/Next Dose for Nivolumab and Combination Nivolumab/Ipilimumab
≤ Grade 1	Asymptomatic TSH elevation*. Patients must be evaluated, endocrine consult. May continue treatment at same dose level at investigator discretion.
Grade 2	Hold until patients are on a stable replacement hormone regimen and symptoms resolve. If treated with steroids, patients must be stable off steroids for two weeks. Resume at same dose level.
Grade 3	Hold until patients are on a stable replacement hormone regimen and symptoms resolve. If treated with steroids, patients must be stable off steroids for two weeks. Resume at same dose level.
Grade 4	Off nivolumab/Ipilimumab treatment.

\*Patients with thyroiditis may be retreated on replacement therapy. Patients must be evaluated to rule out pituitary disease prior to initiating thyroid replacement. Please evaluate pituitary function before beginning steroid therapy or replacement therapy of any kind.

Note all patients with symptomatic pituitary enlargement, exclusive of hormone deficiency, but including severe headache or enlarged pituitary on MRI should be considered grade 3 events. Isolated thyroid or testosterone deficiency may be treated as grade 2 if there are no other associated deficiencies and adrenal function is monitored.

Recommended management: See Endocrine Management Algorithm ([Appendix C](#))

Pneumonitis	Management/Next Dose for Nivolumab and Combination Nivolumab/Ipilimumab	Toxicity management
≤ Grade 1	
Hold dose pending evaluation and resolution to baseline including baseline pO2. Resume no change in dose after pulmonary and/or ID consultation excludes lymphocytic pneumonitis.
	
For Grade 1 (radiographic changes only):
 
 
- Monitor and closely follow up in 2-4 days for clinical symptoms, pulse oximetry (resting and exertion) and laboratory work-up and then as clinically indicated
 
- Consider pulmonary and infectious disease consult
 

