All Grades	
Distinguishing inflammatory pneumonitis is often a diagnosis of exclusion for patients who do not respond to antibiotics and have no causal organism identified including influenza. Most patients with respiratory failure or hypoxia will be treated with steroids. Patients who require steroids should be taken off nivolumab treatment. Bronchoscopy may be required and analysis of lavage fluid for lymphocytic predominance may be helpful. Patients with new lung nodules should be evaluated for sarcoid like granuloma.
 
The investigator is requested to differentiate between non-infectious pneumonitis, and infectious pneumonitis (viral, bacterial, or fungal), aspiration pneumonitis, or other pneumonitis clearly not due to a potential hypersensitivity reaction to the study agent infusions; and provide the basis for his/her assessment that it is infectious or other, as appropriate. The investigator is requested to report with the most specific clinical terms to describe the condition, not simple “pneumonitis”.
	

Additional guidance can be found in the Pulmonary Adverse Event Management Algorithm ([Appendix C](#)). Consider recommending seasonal influenza killed vaccine for all patients.

Fatigue	Management/Next Dose for Nivolumab and Combination Nivolumab/ipilimumab
$\leq$ Grade 1	Continue therapy. No change in dose.
Grade 2	Continue therapy. No change in dose.
Grade 3	Hold until $\leq$ Grade 2. Resume at same dose level.
Grade 4	Off nivolumab/ipilimumab therapy.

Fatigue is the most common adverse event associated with immune checkpoint therapy. Grade 2 or greater fatigue should be evaluated for associated or underlying organ involvement including pituitary, thyroid, and hepatic, or muscle (CPK) inflammation.

Neurologic events	Management/Next Dose for Nivolumab and Combination Nivolumab/ipilimumab
$\leq$ Grade 1	Hold dose pending evaluation and observation. Resume with no change in dose when resolved to baseline.
Grade 2	Hold dose pending evaluation and observation. Hold until baseline. Off protocol treatment if steroids are required. Resume at same dose level

Neurologic events	Management/Next Dose for Nivolumab and Combination Nivolumab/ipilimumab
	for peripheral isolated n. VII (Bell's palsy).
Grade 3	Off nivolumab/ipilimumab treatment.
Grade 4	Off nivolumab/ipilimumab treatment.
Patients who require steroids should be taken off nivolumab/ipilimumab treatment.	

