Patients with any CNS events including aseptic meningitis, encephalitis, symptomatic hypophysitis, or myopathy, peripheral demyelinating neuropathy, cranial neuropathy (other than peripheral n. VII), GB syndrome, myasthenia gravis should be off study.	
Recommended management: See Neurologic Adverse Event Management Algorithm (Appendix C)	

Infusion reaction	Management/Next Dose for Nivolumab and Combination Nivolumab/ipilimumab
≤ Grade 1	No change in dose.
Grade 2	Hold until ≤ Grade 1. Resume at same dose level.
Grade 3	Hold until ≤ Grade 1. Resume at same dose level with pre-medication at the discretion of the PI.
Grade 4	Off treatment
Patients with fever should be evaluated as clinically appropriate. Patients may experience isolated fever during infusion reactions or up to several days after infusion. Evaluation over the course of 1-2 weeks should be done for other autoimmune events that may present as fever.	
The following prophylactic premedications for future infusions: diphenhydramine 25-50 mg (or equivalent) and/or paracetamol 325 to 1000 mg (acetaminophen) at least 30 minutes before additional nivolumab/ipilimumab administrations.	

Fever	Management/Next Dose for Nivolumab and Combination Nivolumab/ipilimumab
≤ Grade 1	Continue therapy. Evaluate and continue at same dose level
Grade 2	Hold until ≤ Grade 1. Resume at same dose level.
Grade 3	Hold until ≤ Grade 1. Resume at same dose level.
Grade 4	Off nivolumab/ipilimumab therapy
Patients with fever should be evaluated as clinically appropriate. Patients may experience isolated fever during infusion reactions or up to several days after infusion. Evaluation over the course of 1-2 weeks should be done for other autoimmune events that may present as fever.	
See table above for Infusion Reactions .	

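### Section 6.1 gives symptomatic Grade 3 hypophysitis two dispositions: resume at the same dose (endocrine table) or go off study (neurologic note)

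*Combined protocol and SAP*

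**What the plan says.** All of the rules below are in Section 6.1 unless stated.

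- **Grading.** The notes to the All Other Events table class as Grade 3 "hypophysitis with symptoms of headache, visual or neurologic changes or radiologic evidence of pituitary enlargement and other CNS events such as aseptic meningitis" or encephalitis. The note under the endocrine table does much the same: "symptomatic pituitary enlargement, exclusive of hormone deficiency, but including severe headache or enlarged pituitary on MRI should be considered grade 3 events".
- **Endocrine table, Grade 3 row.** This table is titled for hypophysitis and adrenal insufficiency. Both checkpoint inhibitors are held until hormone replacement is stable and symptoms have gone, and then: "If treated with steroids, patients must be stable off steroids for two weeks. Resume at same dose level". The Grade 2 row has the same wording.
- **Neurologic events table.** The Grade 3 row stops nivolumab and ipilimumab. A note adds: "Patients who require steroids should be taken off nivolumab/ipilimumab treatment". A further note begins "Patients with any CNS events including aseptic meningitis, encephalitis, symptomatic hypophysitis" and ends by taking all the listed patients off study: "symptomatic hypophysitis, or myopathy, peripheral demyelinating neuropathy, cranial neuropathy (other than peripheral n. VII), GB syndrome, myasthenia gravis should be off study".
- **Hold limit.** "If study treatment is held for >42 days, the patient will go off study".
- **DLT definition (Section 5.2.1).** Grade 3 or higher "non-hematologic toxicity will be considered dose limiting, with the following exceptions"; none of the listed exceptions is hypophysitis.

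**The concern.** The same event, at the same grade, is covered by two instructions that cannot both be followed. An investigator who opens the endocrine table finds a route back to treatment. One who opens the neurologic table finds none. Neither table refers to the other.

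At stake is whether a recovered patient receives both checkpoint inhibitors again or leaves the study. Any restart would be at full dose, because Section 6 permits no nivolumab or ipilimumab reductions. Two sites could each follow the protocol and do opposite things, so a monitor would have no single rule to audit against.

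**Working it through.** This is mainly a comparison of texts. The plan states no figure on this point, so there is none to reproduce.

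**Step 1: do the two rules meet in the same patient?** Yes. Both grading notes put the presentation at Grade 3. The endocrine Grade 3 row then allows a conditional restart, and the neurologic note allows none. Enlargement seen only on MRI, without symptoms, is Grade 3 under the notes but is not clearly symptomatic hypophysitis, so the conflict is confined to symptomatic cases.

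**Step 2: does anything rank them?** The general table defers to exceptions stated below it, which subordinates that table to the specific ones but does not order the endocrine table against the neurologic one. Section 6.2 and the visible text of Appendix C give no order. The Appendix C flowcharts are not shown.

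**Step 3: which way does the wording lean?** Four features favour off study.
- The All Other Events note groups this presentation with other CNS events.
- The neurologic note is the narrower rule (CNS, symptomatic), while the endocrine table covers all hypophysitis and adrenal insufficiency.
- The endocrine Grade 2 and Grade 3 rows are identical, so raising the event to Grade 3 changes no dosing decision inside that table. For dosing, the upgrade matters only where Grade 3 has its own consequence, as in the neurologic table.
- The endocrine rows require stable hormone replacement, whereas the note beneath them describes enlargement apart from hormone deficiency.

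The third feature is not conclusive, because the upgrade also matters for the DLT definition.

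**Step 4: who is affected after the hold limit?** Only patients who meet the restart conditions within 42 days. For those given steroids, two weeks must be steroid-free, leaving 42 − 14 = 28 days for the whole course, taper and symptom resolution. The endocrine taper length is not visible. If it matched the taper of at least 28 days in the pneumonitis table (an assumption), 28 + 14 = 42 days would pass before counting any full-dose period. Few steroid-treated patients could restart on either rule.

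**Step 5: illustrative numbers.** Inputs:
- Triplet maximum (Sections 5.1.2 and 5.1.2.2): 3 levels × 6 + 15 = 33 patients.
- Table 3 (Section 2.1.6): Grade 3–4 endocrine events 2.5%; median time to resolution of Grade 2–4 events 20.1 weeks.

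Results:
- Expected Grade 3–4 endocrine events: 33 × 0.025 = 0.825. Chance of at least one: 1 − 0.975^33 = 0.57.
- Share resolved within 42 days (6 weeks), assuming exponential times: 1 − 2^(−6/20.1) = 0.187.
- Product: 0.825 × 0.187 = 0.154 patients.

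These are illustrations and not limits. Table 3 is for ipilimumab 10 mg/kg in melanoma, while this trial gives 1 mg/kg within a three-drug regimen. The rate pools all endocrine events and includes Grade 4. Symptom resolution on stable replacement may also come sooner than resolution of the event.

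**Step 6: DLTs.** A drug-related Grade 3 hypophysitis in cycle 1 is dose limiting under Section 5.2.1 whichever table is followed. Later events do not enter escalation decisions (Section 5.1.2.1).

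**The case against.** The strongest reply is that a careful reader would reach off study anyway: the specific rule prevails over the general one, it is the cautious choice, and the endocrine rows are written for hormone deficiency. Much of this stands. A reader might infer that the plan leaves the direction entirely open, and Step 3 shows that it does not. What survives is that the endocrine table names hypophysitis, waits for symptoms to resolve, carries a note placing symptomatic enlargement in Grade 3 and adds no stop. Someone working from that table alone has a written instruction to resume.

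A second reply is that the Appendix C endocrine and neurologic algorithms may settle the matter. That cannot be excluded. It lowers confidence but does not remove the conflict between the two visible rules.

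A third is that investigators may stop treatment whenever continuing would carry substantial clinical risk. This is a real safeguard, but it depends on case-by-case judgement and does not say which table applies.

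**Conclusion.** The inconsistency is real and minor. Two stated rules give incompatible dispositions for one Grade 3 presentation, with the text leaning towards off study. The effect is on safety and disposition of the few patients who could meet the endocrine restart conditions within 42 days. The expected number is likely below one, on the assumption that Table 3 is a rough guide; the documents give no hypophysitis-specific rate and do not allow a bound. The two figures in Step 5 should not be read as the ends of a range.

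A reader might also infer an effect on DLT counts: if symptomatic hypophysitis in the neurologic note reached Grade 2 cases managed with hormone replacement, removal would be a permanent discontinuation and so a DLT, while the endocrine Grade 2 row would resume treatment. The documents do not support this reading. The neurologic sentence is confined to CNS events, and the CNS-type presentation is already Grade 3 under both grading notes. Escalation and sample size are unaffected.

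Confidence is moderate because the Appendix C algorithms could not be checked.

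**What to change.** Keep the neurologic note as it is. Add this clause to the endocrine Grade 3 row and repeat it in the note beneath that table: *except hypophysitis with headache, visual or neurologic changes or symptomatic pituitary enlargement, which goes off study per the Neurologic events note*. Hold-and-resume then remains for hormone-deficiency hypophysitis. The Appendix C endocrine and neurologic algorithms should be checked for agreement at the same time.

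The cost is one clause in two places at the next amendment, with no change to the DLT definition, escalation rules or sample size. The clinical downside is that a rare patient who recovers within the hold limit can no longer be rechallenged.

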### Cardiac Toxicities Nivolumab and combination of nivolumab/ipilimumab

- Drug will be held for any indication suggestion of cardiac dysfunction of any grade pending evaluation.
- For patients with evidence of CHF, MI, cardiomyopathy, or myositis cardiac evaluation including lab tests and cardiology consultations as clinically indicated including EKG,

CPK, troponin, ECHO cardiogram. Drug will be held for grade 2 cardiac dysfunction pending evaluation.

- Drug will be permanently discontinued for grade 3 or 4 cardiac dysfunction and grade 2 events that do not recover to baseline or that reoccur.
- Treatment as clinically indicated for cardiomyopathy.

Cardiac 	Management/Next Dose for Nivolumab and Combination Nivolumab/ipilimumab
≤ Grade 1	Hold dose pending evaluation and observation.  Evaluate for signs and symptoms of CHF, ischemia, arrhythmia or myositis.  Obtain history EKG, CK (for concomitant myositis), CK-MB. Repeat troponin, CK and EKG 2-3 days. If troponin and labs normalize, may resume therapy. If labs worsen or symptoms develop, then treat as below.
Grade >2 with suspected myocarditis	Hold dose.  Admit to hospital. Cardiology consult. Rule out MI and other causes of cardiac disease. Cardiac Monitoring. Cardiac Echo. Consider cardiac MRI and cardiac biopsy. Initiate high dose methylprednisolone. If no improvement within 24 hours, add either infliximab, ATG or tacrolimus. Resume therapy if there is a return to baseline and myocarditis is excluded or considered unlikely.
Grade >2 with confirmed myocarditis	Off protocol therapy. Admit to CCU (consider transfer to nearest Cardiac Transplant Unit). Treat as above. Consider high dose methylprednisolone. Add ATG or tacrolimus if no improvement.

Including CHF, LV systolic dysfunction, myocarditis, CPK, and troponin.

Patients with evidence of myositis without myocarditis may be treated according to “all other events”.

Unexplained atrial arrhythmias, new onset atrial fibrillation, conduction abnormalities, and focal cardiomyopathy (Takasubo) may be associated with myocarditis even with normal echocardiograms. These events may require evaluation with a cardiac MRI to confirm myocarditis when clinically indicated.

Myositis may occur with myocarditis and/or Guillain Barre syndrome.

**Note:** The optimal treatment regimen for immune-mediated myocarditis has not been established. Since this toxicity has caused patient deaths, an aggressive approach is recommended.

Recommended management: See Myocarditis Management Algorithm ([Appendix C](#))

Neutropenia	Management/Next Dose for Ipilimumab and Combination Nivolumab/ipilimumab
≤ Grade 1	No change in dose
Grade 2	Hold until ≤ Grade 1. Resume at same dose level.
Grade 3	Hold* until < Grade 2.
Grade 4	Off protocol therapy

\*Patients requiring a delay resulting in >2 missed doses should go off protocol therapy.

Thrombocytopenia	Management/Next Dose for Ipilimumab and Combination Nivolumab/Ipilimumab
≤ Grade 1	No change in dose
Grade 2	Hold until ≤ Grade 1. Resume at same dose level.
Grade 3	Hold* until < Grade 2.
Grade 4	Off protocol therapy

\*Patients requiring a delay of >2 weeks should go off protocol therapy.

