### 7.1 Comprehensive Adverse Events and Potential Risks List (CAEPR)

#### 7.1.1 CAEPR for Ipilimumab

#### Comprehensive Adverse Events and Potential Risks list (CAEPR) for Ipilimumab (MDX-010, NSCs 732442 and 720801)

The Comprehensive Adverse Events and Potential Risks list (CAEPR) provides a single list of reported and/or potential adverse events (AE) associated with an agent using a uniform presentation of events by body system. In addition to the comprehensive list, a subset, the Specific Protocol Exceptions to Expedited Reporting (SPEER), appears in a separate column and is identified with bold and italicized text. This subset of AEs (SPEER) is a list of events that are protocol specific exceptions to expedited reporting to NCI (except as noted below). Refer to the 'CTEP, NCI Guidelines: Adverse Event Reporting Requirements'  
[http://ctep.cancer.gov/protocolDevelopment/electronic\\_applications/docs/aeguidelines.pdf](http://ctep.cancer.gov/protocolDevelopment/electronic_applications/docs/aeguidelines.pdf) for further clarification. *Frequency is provided based on 2678 patients.* Below is the CAEPR for Ipilimumab (MDX-010).

**NOTE:** Report AEs on the SPEER **ONLY IF** they exceed the grade noted in parentheses next to the AE in the SPEER. If this CAEPR is part of a combination protocol using multiple investigational agents and has an AE listed on different SPEERs, use the lower of the grades to determine if expedited reporting is required.

Version 2.10, March 29, 2019

Adverse Events with Possible Relationship to Ipilimumab (MDX-010) (CTCAE 5.0 Term) [n= 2678]			Specific Protocol Exceptions to Expedited Reporting (SPEER)
Likely (>20%)	Less Likely (<=20%)	Rare but Serious (<3%)	
BLOOD AND LYMPHATIC SYSTEM DISORDERS			
		Blood and lymphatic system disorders - Other (acquired hemophilia)	
CARDIAC DISORDERS			
	Atrial fibrillation		
		Myocarditis 	
		Pericardial effusion	
EAR AND LABYRINTH DISORDERS			
	Hearing impaired		
ENDOCRINE DISORDERS			
	Adrenal insufficiency 		
	Hyperthyroidism 		
	Hypophysitis 		
	Hypopituitarism 		
	Hypothyroidism 		
	Testosterone deficiency 		
EYE DISORDERS			
	Eye disorders - Other (episcleritis) 		
	Uveitis 		
GASTROINTESTINAL DISORDERS			
	Abdominal pain		
	Colitis 		Colitis  (Gr 3)
		Colonic perforation 	
	Constipation		
Diarrhea			Diarrhea (Gr 3)

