### **13.2 Sample Size/Accrual Rate**

With an anticipated accrual of 3-4 patients per month, it is expected that accrual can be completed in 16 months. The minimum number of patients enrolled in this trial will be 15 and the maximum number of patients enrolled will be 45, including an expansion cohort of 15 patients that will be treated at the MTD or the maximum administered dose. To allow for unevaluable patients, the accrual ceiling has been set at 50 patients.

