## APPENDIX C: MANAGEMENT ALGORITHMS FOR ADVERSE EVENTS

### **Management Algorithms for Gastrointestinal, Renal, Pulmonary, Hepatic, Endocrinopathy, Skin, Neurological, and Myocarditis Adverse Events**

[figure not shown]
Please note that in some cases the treatment algorithms recommend steroids if symptoms do not resolve in 7 days. However, this recommendation is not meant to delay steroid treatment at any time it is clinically indicated.

Any patient started on corticosteroids initially who is determined to not require steroid treatment for an autoimmune adverse event may resume therapy after a 2-week observation period without further symptoms at the discretion of the PI or investigator.

**Note:** All treatment algorithms should be interpreted in the context of CTCAE v5.

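### Section 6.1 gives opposite rechallenge instructions for a recovered Grade 3-4 cardiac event in which myocarditis was suspected and then ruled out or judged unlikely

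*Combined protocol and SAP*

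**What the plan says.** Both rules are in Section 6.1, under the heading on cardiac toxicities of nivolumab and of the nivolumab/ipilimumab combination.

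- **Bullet.** "Drug will be permanently discontinued for grade 3 or 4 cardiac dysfunction". The same sentence also stops drug for Grade 2 events that fail to recover or that come back. Recovery is a condition for Grade 2 events only.
- **Table, suspected-myocarditis row (above Grade 2).** Hold the dose, admit, work up and give high-dose methylprednisolone. Then: "Resume therapy if there is a return to baseline and myocarditis is excluded or considered unlikely".
- **Table, confirmed-myocarditis row (above Grade 2).** The patient comes off protocol therapy.
- **Table, footnote 1, on scope.** "Including CHF, LV systolic dysfunction, myocarditis, CPK, and troponin".
- **Note under the table, on immune-mediated myocarditis.** "Since this toxicity has caused patient deaths, an aggressive approach is recommended".

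The introduction to Appendix C adds a general permission. A patient started on corticosteroids who turns out not to need them for an autoimmune event "may resume therapy after a 2-week observation period without further symptoms at the discretion of the PI or investigator".

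**The concern.** Two cardiac-specific rules for the same drugs appear to give opposite answers for the same patient. If so, investigators could act in opposite ways after a serious cardiac event, and each could cite the protocol.

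The more worrying direction is rechallenge. Once the patient is back at baseline, the table needs myocarditis only to be thought unlikely, and it asks the team merely to consider cardiac MRI and biopsy. A patient with some remaining diagnostic doubt could be re-exposed to two checkpoint inhibitors although the bullet forbids it. In the other direction, a patient whose event had a different cause and resolved could lose treatment that the table would have allowed.

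**Working it through.** The question is one of text, so the check sets the two rules side by side for each kind of Grade 3-4 event.

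| Grade 3-4 event | Bullet | Table | Result |
|---|---|---|---|
| Confirmed myocarditis | Stop permanently | Off protocol therapy | Agree |
| CHF or LV dysfunction, myocarditis suspected, not back to baseline | Stop permanently | Resumption condition not met | No conflict |
| CHF or LV dysfunction, back to baseline, myocarditis excluded | Stop permanently | Resume | **Conflict** |
| CHF or LV dysfunction, back to baseline, myocarditis judged unlikely | Stop permanently | Resume | **Conflict** |
| Isolated CPK or troponin rise, myocarditis suspected then excluded | Arguably not dysfunction | Resume | Need not conflict |
| Cardiac dysfunction, myocarditis never suspected | Stop permanently | No matching row | Bullet alone applies |

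The overlap depends on footnote 1. Without it, the table might be read as covering only enzyme rises. With CHF and LV systolic dysfunction named there, it covers the same events as the bullet.

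**Does the grade label matter?** The table has a row for Grade 1 or below and rows for grades above 2, so Grade 2 has no row, and the label may be a slip for Grade 2 and above. Grades 3 and 4 stay in the row on either reading, so the conflict remains.

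**Does other text settle it?** The table in Section 6.1 for all other events takes patients off therapy at Grade 4, and at Grade 3 unless the event is immune-related, but both rules defer to exceptions noted below them. That returns the reader to the cardiac section. The visible text of the Appendix C myocarditis algorithm does not address resumption. Its figure is not shown in the copy reviewed.

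**Effect on the primary endpoint.** Section 5.2.1 makes Grade 3 or higher non-hematologic toxicity dose limiting, and none of its exceptions is cardiac. Section 5.2.3.1 adds events that require steroids, with narrow exceptions, and events that require permanent discontinuation. A drug-related Grade 3-4 cardiac event in cycle 1 therefore counts as a DLT whichever rechallenge rule is followed.

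**Scale only.** The ipilimumab and nivolumab risk lists in Section 7.1 both place myocarditis in the band below 3%. Section 13.2 states that "the accrual ceiling has been set at 50 patients". Assuming a rate p of 1% to 3%:

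- Expected cases = 50 × p: 50 × 0.01 = 0.5, up to 50 × 0.03 = 1.5.
- Chance of at least one case = 1 − (1 − p)^50: 1 − 0.99^50 = 0.39, up to 1 − 0.97^50 = 0.78.

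These figures describe myocarditis itself. The patients in conflict are those in whom it was suspected and then excluded or thought unlikely, and the documents give no rate for them. Nor do the lists describe the three-drug combination.

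**The case against.** The best case for the plan is that a workable reading exists. The opening of Section 6.1 sends patients who do not meet the criteria to resume to the management tables, which suggests that the tables govern. The suspected-myocarditis row is the more specific path while the diagnosis is open. It requires steroids, so the Appendix C permission, whose heading names myocarditis, reaches this patient once myocarditis is excluded. If the grade label is a slip for Grade 2 and above, the resumption sentence also has a Grade 2 population in which nothing conflicts. The missing Appendix C figure might state the rule outright.

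There are safeguards too. An investigator who sees substantial clinical risk in continued dosing should stop nivolumab and ipilimumab. A patient held for more than 42 days goes off study. An unexpected, at least possibly related Grade 4 or 5 event halts the protocol. The team discusses every patient weekly.

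Much of this is accurate, but it does not remove the conflict. The pointer to the tables is general and is not a precedence clause. The bullet is equally cardiac-specific and carries no qualifier. The Appendix C permission supports the table and so contradicts the bullet; it does not reconcile the two. The Grade 2 reading explains why the sentence might be there, but it does not take Grades 3 and 4 out of the row. The safeguards limit harm, yet none says whether a recovered Grade 3-4 patient may be rechallenged.

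Three limits stand: the trigger is rare, escalation is essentially unaffected, and the myocarditis counts do not measure the affected group.

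**Conclusion.** The concern holds. For recovered Grade 3-4 cardiac dysfunction in which myocarditis was suspected and then excluded or thought unlikely, Section 6.1 both forbids and permits a return to nivolumab/ipilimumab. Confirmed myocarditis is handled consistently, and isolated enzyme rises need not conflict.

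The number of patients is small and cannot be estimated from the documents. The conclusion rests on the visible text; the Appendix C myocarditis figure could not be checked, and a rule there would still leave the bullet and the table disagreeing. No effect on sample size, DLT counts or the MTD is claimed. The point should be corrected because the decision concerns re-exposure after a possibly fatal toxicity.

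**What to change.** Make one rule govern recovered Grade 3-4 cardiac dysfunction, in one of two ways:

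1. Remove the resumption sentence for Grade 3-4 dysfunction from the suspected-myocarditis row. This matches the bullet and is the safer default.
2. Keep resumption, and add to the bullet an explicit exception for events that return to baseline with myocarditis excluded. In that case, state whether the 2-week observation period in Appendix C applies, since the row mentions none.

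In the same edit, confirm whether the row is meant to start above Grade 2 or at Grade 2. Carry the bullets' existing Grade 2 rule into the table: hold pending evaluation, and stop if the event does not recover or comes back. Check that the Appendix C myocarditis figure agrees.

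The cost is protocol wording in one bullet and one table. Endpoints, sample size and escalation rules do not change.
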